***Addiction Dimensions for Assessment and Personalised Treatment** (ADAPT [53]). The ADAPT is a clinician completed 14-item instrument used for drug addiction treatment planning and outcome evaluation with three-subscales: opioid addiction severity, coexisting health and social problems, and recovery strengths.

***Clinical Global Impression** (CGI-S and I; [36]). The CGI is a single item clinician assessment of disorder severity and improvement.

Craving Experience Questionnaire (CEQ-F [frequency] [56]). The CEQ-F will be completed for opioids (CEQ-F[H] and cocaine (CEQ-F[C]). This scale has a 14-day recall period and captures intensity, imagery, and intrusiveness aspects of drug craving.

Visual analogue scale of maximum need (VAS-N[H/C] and want (VAS-W[H/C]). These single item (0-100) rating scales have a recall period of the past 14 days.

Difficulties in Emotion Regulation Scale – Short Form (DERS-SF; [37]). The DERS The DERS is an 18 item self-report scale which records current emotional dysregulation in six subscales: non-acceptance, goals, impulse, aware, strategies and clarity.

QIDS-SR ([39]) The QIDS-SR is a brief scale which assesses the frequency of depressive symptoms during in past two weeks.

Work and Social Adjustment Scale (WSAS; [38]). The WSAS is a 5-item scale which records the extent of social functioning impairment perceived to be caused by OUD in the past two weeks.

Service User Recovery Evaluation (SURE; [6]). The SURE is a patient-reported outcome measure and is a multi-dimensional measure of perceived recovery status.

Patient reported outcome measure - Status (PRO-S and I). The PRO-S is a single 7-point item assessment of the extent to which the participant perceives the severity of their opioid-related problems at baseline and at follow-up.

EQ-5D-5L ([39])The EQ-5D-5L is a brief generic scale which captures health status on five dimensions: mobility, self-care, usual activities, pain/discomfort, anxiety/depression, and with a 20cm vertical visual analogue scale. These responses generate health profiles from which health utilities can be calculated for economic evaluations.

Alcohol and Drug Service Use Schedule (ADSUS). The ADSUS is a well-developed structured patient interview that records use of health, social, welfare and criminal justice services and crime. The ADSUS was successfully used in the ARC trial.

Keyworker Contact Form (KCF). The KCF records the clinical team's direct and indirect time working on EXPO.

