10.3 Procedures for assessing efficacy parameters

Endpoint data collection will be gathered during 13 clinic visits using the TOP (timeline follow-back [TLFB] interview) and will also include recording of cocaine and non-medical benzodiazepines. All participants will be asked to provide a urine sample during each visit. If the participant does not take a UDS then all tested drugs will be taken to be positive for the past 3 days.

10.a Assessment of Cost Effectiveness

10.1a Primary Economic Parameter

The primary economic endpoint will be the incremental cost per quality-adjusted life year (QALY) gained of injectable depot maintenance buprenorphine versus standard oral therapy, adopting a broad societal cost perspective. Incremental costs will be determined from responses to the ADSUS questionnaire and the EXPO keyworker contact form. QALYs will be calculated from EQ-5D-5L scores and by applying the EQ-5D-3L crosswalk value set. This has no implications for the sample size calculation.

10.2a Secondary Economic Parameters

There will be 2 secondary economic parameters:

- (1) Health profiles (EQ-5D-5L);
- (2) Quantities of resource use (ADSUS) and total costs disaggregated by broad categories;

10.3a Procedures for assessing cost-effectiveness parameters

The cost utility analysis will consider patient QALYs and costs from a broad societal perspective including NHS and personal social services, productivity losses (including time off work because of illness), and criminal activity. This will be based on an incremental analysis of the mean costs and QALYs for injectable depot maintenance buprenorphine versus standard oral therapy.

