The number of QALYs experienced by each participant will be calculated as the area under the curve, using the trapezoidal rule, and adjusted for baseline [46]. Total costs and QALYs will be used to calculate the incremental cost-effectiveness ratio of injectable depot maintenance buprenorphine versus standard oral therapy. Data that are assumed missing at random will be imputed using multiple imputation by chained equations as will be specified in the HEAP. Non-parametric bootstrapped 95% central ranges for items of resource use, costs and QALYs will be estimated (10,000 replicates).

A range of one-way sensitivity analyses will be conducted to test whether, and to what extent, the incremental cost-effectiveness ratio is sensitive to key assumptions in the analysis (e.g. unit prices). Multivariate sensitivity analyses will be applied where interaction effects are suspected, and the joint uncertainty in costs and benefits will be considered through application of bootstrapping and estimation of cost-effectiveness acceptability curves [47]. Alternative scenarios will be specified in the HEAP and will include consideration of a narrower cost perspective (NHS +/- personal social services) to enable comparison with the NICE threshold range of £20,000 to £30,000 per QALY.

A Health Economic Analysis Plan (HEAP) [48] (agreed prior to the analysis), will define the analytic steps to be undertaken. The economic findings will be reported according to the CHEERS guideline [49].

13. Trial Steering Committee

A TSC will operate independently from the Trial Management Group (TMG), the study funder (Indivior), and the Co-sponsors (King's College London and South London and Maudsley NHS Foundation Trust). The TSC's key purpose will be to ensure the overall integrity of the study. Committee membership will be documented in the first (joint) minutes of the TSC and DMC.

14. Data Monitoring Committee

The DMC's key purpose (as set out in DAMOCLES) will be defined in the DMC charter. Reports to the DMC will be prepared and presented by the Trial Statistician.

15. Trial Management Group

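### Protocol 12.2 states a baseline adjustment for QALYs but none for costs, although AD-SUS is collected at baseline; the protocol or HEAP should settle this before data lock

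*Protocol*

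**What the plan says.** Protocol 12.2 (Assessment of Cost Effectiveness) describes QALYs as an area under the curve "using the trapezoidal rule, and adjusted for baseline". The title of the reference it cites there concerns baseline utility. The next sentence reads "Total costs and QALYs will be used to calculate the incremental cost-effectiveness ratio of injectable depot maintenance buprenorphine versus standard oral therapy". Nothing comparable to the QALY adjustment is attached to costs.

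Protocol 10.3a says the cost-utility analysis is "based on an incremental analysis of the mean costs and QALYs for injectable depot maintenance buprenorphine versus standard oral therapy". It names no covariates. Its primary perspective is societal and includes "productivity losses (including time off work because of illness), and criminal activity".

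AD-SUS, per Protocol 9.1, "records use of health, social, welfare and criminal justice services and crime". The schedules in Protocol 9.2 and SAP Table 1 both mark it at baseline, and SAP Table 1 repeats it at weeks 12 and 24.

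Randomisation is stratified by site and injecting status (Protocol 8.4). The covariates listed in Protocol 12.2 for the regression models fall under Assessment of Efficacy and are not carried into the economic text.

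Remaining detail is left to the HEAP, which is to be "agreed prior to the analysis), will define the analytic steps to be undertaken". SAP 5.2 adds that the HEAP will align with the SAP and be signed off before data lock.

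**The concern.** A cost-effectiveness ratio has two random components, and the protocol tells the reader how baseline is handled for only one of them. The cost component includes crime, service use and lost productivity. If a participant's costs before randomisation predict costs afterwards, two things follow when the cost difference is left unadjusted. Any chance difference between arms in prior cost carries partly into the incremental cost. The bootstrap ranges and the acceptability curve are also wider than the data require. Randomisation does not stratify on prior cost or crime, so balance there is left to chance.

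The QALY difference over 24 weeks may be small, and a small denominator magnifies any shift in cost. Leaving the choice open also allows adjusted and unadjusted costs to be compared before one of them is presented as primary.

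**Working it through.** **Inputs from the documents**
- Planned size: 152 per arm for Group 1 versus Group 2 (Protocol 5.2). I assume the economic comparison uses these two arms, since the protocol does not name the groups.
- AD-SUS at baseline (Protocol 9.2, SAP Table 1).
- Not given: the cost SD, the baseline to follow-up cost correlation r, the expected QALY gain and the AD-SUS recall period. All values used for these are assumptions.

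**The plan's own sample size.** The two-arm Poisson formula is n per arm = (1.960 + 1.282)² × [1/(λ₀t) + 1/(λ₁t)] / (ln 1.23)². I use λ₀ = 0.6, λ₁ = 0.6 × 1.23 = 0.738 and t = 161/28 = 5.75 (my reading of the rate as per month). This gives 128.85, so 129 per arm and 258 in total; 258/0.85 = 303.5, rounded up to 304. The stated 304, or 152 per arm, reproduces. It is used here only to size chance imbalance and does not bear on whether the point is right.

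**Chance imbalance in baseline cost.** In baseline SD units, SE = √(2/152) = 0.115, with a 95% range of ±1.96 × 0.115 = ±0.225. Because baseline AD-SUS is scheduled for everyone and multiple imputation is planned, 152 is a better basis than the post-attrition 129, for which SE = √(2/129) = 0.125. If stratification explains some baseline cost, the imbalance would be a little smaller.

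**Effect on the cost difference.** Given a baseline imbalance d, the unadjusted difference is expected to move by r × d, in follow-up SD units. Linear baseline adjustment removes that shift and multiplies the variance by 1 − r². The equivalent gain in sample size is 1/(1 − r²) − 1.

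| Assumed r | Shift at 1 SE (SD) | Shift at 1.96 SE (SD) | Variance cut | SE: unadjusted → adjusted (SD) | Equivalent extra participants |
|---|---|---|---|---|---|
| 0.3 | 0.034 | 0.067 | 9% | 0.115 → 0.109 | 10% |
| 0.5 | 0.057 | 0.112 | 25% | 0.115 → 0.099 | 33% |
| 0.6 | 0.069 | 0.135 | 36% | 0.115 → 0.092 | 56% |

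These figures count baseline cost only. Any gain from centre and injecting status would be additional.

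**What this could mean for the ratio (illustration only).** Holding the QALY gain fixed, shift in ratio = r × 0.1147 × cost SD / QALY gain. With an assumed cost SD of £10,000 and a one-SE imbalance:
- QALY gain 0.02: about £17,200, £28,700 or £34,400 per QALY at r = 0.3, 0.5 or 0.6.
- QALY gain 0.05: about £6,900, £11,500 or £13,800.

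Halving the SD halves every figure. For scale, Protocol 12.2 cites £20,000 to £30,000 per QALY as the comparison range for its narrower cost perspective.

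**The case against.** A reader might infer that the trial will use raw costs. The documents do not say so. Using total costs to form a ratio does not exclude a regression-based increment, and the analytic steps are left to an unseen HEAP. That HEAP must align with a SAP whose section 6.7 puts centre and injecting status in every secondary-outcome model, and the baseline score in continuous-outcome models. This stands: the gap is one of specification, not a demonstrated choice. It does not close the point, because the protocol settles the QALY adjustment itself and leaves its cost counterpart unstated.

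A reader might also infer that baseline imbalance passes straight into the ratio, or that the ratio is biased. Neither follows. Only the fraction r carries through, so full transmission needs r = 1. Under randomisation the unadjusted cost difference is unbiased on average.

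The different treatment of the two sides has some logic. Baseline utility is arithmetically part of an area-under-the-curve QALY, whereas cost before randomisation is not described as part of the follow-up total. Adjusting costs is therefore mainly a gain in precision and in conditional balance, and does not repair the same defect.

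Heavy tails and persistence of crime and hospital costs are plausible but are not documented. High costs that first arise during follow-up would not be removed by baseline adjustment. Keyworker-form costs have no baseline mark in either schedule, so baseline AD-SUS cannot mirror total cost, and r may be modest.

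Finally, bootstrapping and acceptability curves already express sampling uncertainty, and the narrower perspective tests dependence on crime costs. But bootstrapping an unadjusted difference neither corrects the point estimate for an observed imbalance nor recovers the lost precision, and the sensitivity analyses that are named do not include baseline cost.

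**Conclusion.** The point holds as a gap in specification with a worthwhile, nearly free remedy. Protocol 12.2 specifies baseline adjustment for QALYs and states none for costs. The economic text names neither randomisation factor, and baseline AD-SUS data are available. Whether the HEAP fills the gap cannot be told from the documents.

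At assumed r of 0.3 to 0.6, what is at stake is 9% to 36% of the variance of the cost difference, and a shift of about 0.03 to 0.07 SD for a one-standard-error imbalance at 152 per arm. These sizes rest on an assumed r, a linear relation between baseline and follow-up cost, and economic arms equal to Groups 1 and 2. If r is low the gain is small. The per-QALY figures are illustrations of scale, not predictions.

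**What to change.** State in Protocol 12.2 or the HEAP, before data lock:
- Incremental costs are estimated by a regression on arm, baseline AD-SUS cost, centre and injecting status.
- Incremental QALYs are estimated by a regression on arm, baseline utility, centre and injecting status.
- The two are fitted jointly, for example by seemingly unrelated regression or an equivalent method, and the bootstrap is applied to that joint model.
- The raw cost difference is reported descriptively.

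If the HEAP already says this, a cross-reference in Protocol 12.2 is enough.

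The cost is wording and a little analysis time, with no new data. Two checks belong with it: that the baseline and follow-up AD-SUS recall windows are comparable, and that the text acknowledges keyworker-form costs have no baseline counterpart. The main downside is that the gain will be slight if baseline cost predicts follow-up cost poorly.

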		
Amendment to research measures utilised and the timepoints of collection.
 
Section 10.1 and 10.2 Clarification and additional primary and secondary efficacy parameters set.
 
Section 11.2 All SARs in the XR-Bup IMP groups are unexpected and will be reported as SUSARS in the study.
 
Amendment to sample size and statistical analysis to be conducted.
 
Section 25 Signatures added for Co-Lead Investigator and Trial Statistician.

2.0	08.01.2020	
Clarification/expanding/amending minor instructions and details across the protocol.
 
Section2 Addition of PI contact details.
 
Section 5.2 Addition of new recruiting site.
 
Section 6.2 Removal of Buprenorphine Naloxone- Bup-NX (Suboxone) as an active comparator.
 
Section 6.3 Dosing guidance for participants who consent to receive more than 6 doses of XR-Bup.
 
Section 6.4 Amendment of the numbering of injection sites to be consistent across guidance given, PIL, database. Cold press is authorised upon injection.
 
Section 6.6 Removal of XR Bup to be recorded as an Important Medical Event (IME).
 
Section 6.8.1 Removal of instruction that IMP can be stored at room temperature for up to 7 days prior to administration.
 
Section 7.0 Clarity and addition information on timetable of sessions and information regarding withdrawals.
 
Section 8.1 Reducing Met from 50mg to 30mg/day or less for inclusion into the trial. Significant change of wording of inclusion criterions 7 and 8. Clarity of other inclusion/exclusion criterions.
 
Section 8.3 Removing the induction process for participants new to treatment as all participants are to be already in receipt of opioid substitution therapy. Clarification of the induction process for all participants randomised to XR-Bup.
 
Section 9.1 Detailing optional consent for an Exit Interview with participants randomised to XR-Bup at South London recruiting centre.
 
Section 9.2 Adding timeline for procedures to be conducted with XR-Bup participants who consent to additional treatment. Adding timeline for Exit Interview. Change in payments to include payments at all visits.
 
Section 9.3

		
Change of procedure of collection of LFT blood test as only required for XR-Bup participants. Use of past blood results if available at screening.
 
Section 10.2 Additional secondary efficacy parameters added to trial outcomes measures.
 
Section 10.3 Error in number of trial visits from 10 to correct number of 13. Removal of alcohol consumption collected as endpoint data collection.
 
Section 11.1 Clarity of procedure as per section 9.3.
 
Section 12.2 Clarify of analysis.
 
Section 15. Change of membership of TMG to remove site staff.
 
Section 24 Signatures added for all PI's to confirm review and approval of protocol.
 
Section 25 Addition of summary table of changes between protocols.

2.1	09.07.2020	
Section 7 Removing instruction that the PI and lead therapist will meet weekly to discuss case management of non-PSI participants.
 
Section 9.1.2 Amendment of sub-section heading Exit Interview to be conducted at Newcastle, West Midlands and Tayside in addition to South London.
 
Section 9.2 Details of Exit Interview.
 
Section 12.1 Correction of Typographical error from 4 to 5 sites.
 
Section 24 Signature space for [name] PI at Tayside study centre.

3.0	22.07.2020	
Section 6.2 Addition of Buprenorphine Naloxone [Bup-NX (Suboxone)] as an active comparator as this is routinely prescribed at the Tayside Site as standard of care medication for OUD.
 
Section 9.2 Additional details of Exit Interview.

4.0	30.09.2020	
Section 6.2 Addition of Espranor® (Esp) as an active comparator as this is routinely prescribed at the Tayside Site as standard of care medication for OUD. Clarity that participants randomised to group 2 and group 4 are permitted to change between the active comparator drugs whilst enrolled in the trial by following the prescribing guidelines as detailed in the SmPC and if there are no known allergic, adverse reactions or contraindications to the drug.
 
Section 6.3 Esp usual daily dose separated from Bup as max daily is 18mg.
 
Section 6.8.2 Addition of Bup-NX and Esp.

		
Section 8.1 and 8.2 Updated Inclusion and Exclusion Eligibility criteria to include Bup NX and Esp. Clarity that participant is ineligible if they have any allergic or adverse reactions or contraindication to Buprenorphine. If participant has any allergic or adverse reaction or contraindication to Met or naloxone, or excipients of Bup-NX or Esp they can be prescribed Bup within the trial.
 
Section 11.2 Updated reference dates for the Trial Specific Addendum to the Reference Safety Information for The Investigator's Brochure (IB; RBP-6000; Indivior 06 March 2020; pages 144-153).

5.0	01.06.2021	
Section 2 Updated clinic name at Tayside study site.
 
Section 3 Updated abbreviations for new terms introduced within the protocol.
 
Section 5.2 Caveat to document new recruitment phase timelines.
 
Section 5.3 Caveat to document amendment to study analysis timelines.
 
Section 6.5 Removal of reference to EXPO Trial Specific Addendum to Reference Safety Information as the Investigator Brochure has been updated to incorporate this information. Therefore, no requirement for the Addendum.
 
Section 9.1 Correction of Typo from clinician version to research version (SCID-5-RV) Addition of measurements OSTQOL; PHQ-15 and PHQ4. Confirmation that where document as clinician administered measure this can be delegated to a health care worker after the baseline/screening assessment. Exit Interview qualitative interview based on ADAPT measurement. Details what the Bup/Met +PSI and Extension Phase Interview comprise of
 
Section 9.2 Addition of timepoints for Bup/Met + PSI Interview and Extension Phase Interview. Due to the Coronavirus 2019 (COVID-19) pandemic and to limit health care contacts, week 2, 6, 10, 14, 18 and 22 visits are permitted to be conducted via telephone if required. In this instance a UDS may not be obtained. Missed UDS due to visits being conducted by telephone are not considered a protocol deviation and do not have to be recorded on the deviations log however missed UDS for all other reasons should be recorded. All other visits are to be conducted in person at the study centre.
 
Section 9.3 Clarification that participants can continue in the trial if LFT bloods are not taken post randomisation based on PI/Sub Investigator clinical judgement.
 
Section 10.2 CUD remission status added as an efficacy parameter (previously omitted due to error but already approved as a measure). Addition of 2 secondary efficacy parameters for the measures/outcomes being collected within the Exit Interview, Bup/Met + PSI Interview and Extension Phase Interview.
 
Section 11.1 Clarification that participants can continue in the trial if LFT bloods are not taken post randomisation based on PI/Sub Investigator clinical judgement.

			Section 5.1	Table updated in line with latest protocol version
			Section 5.2	Text added to summarise missing data due to administration error (i.e. missing days off end of some participant TLFB due to final visit

		being conducted early) and use of medical notes and rule for where this has occurred
	Section 5.2 other measures	PHQ-15, PHQ4 and OSTQOL added for exit interviews
	Section 5.3	Update to text to clarify safety data being reported in final analysis report
	Section 6	Analysis timelines updated
	Section 6.8	Detail on sub group analysis added in
	Section 6.9	Updates to sensitivity analysis; Addition of UDS missing data sensitivity analysis, Clarification of per protocol and mITT and addition of 14-day TLFB truncated analysis for administration error.
4 [name]		Addition of sensitivity analysis for Grace period
	Acronym table and throughout document	XR-Bup amended to BUP-XR Met amended to MET Bup amended to BUP-SL Esp emended to ESP
	Section 3.1	Background text updated to align with latest protocol
	Appendix 2	Adjustments to scoring of CEQ-F, WSAS and SURE to align with correct scoring.
	Appendix 3 6.1 Analysis timeframe	Addition of MOCA scoring Update to planned analysis timelines
	5.2 Definitions and calculations of outcome measures	Clarification that objective 3, measure 3 will not be conducted as part of the analysis within this SAP
	6.9 Sensitivity analyses or model testing	Table 3 dates of UDS collection updated Update of grace period sensitivity from day 0 to 161 to day 0 to 168

1. ACRONYMS AND DEFINITION OF TERMS

Acronym	Meaning
ADAPT	Addiction Dimensions for Assessment and Personalised Treatment
AD-SUS	Alcohol and Drug Service Use Schedule
AE	Adverse Event
ALC-QFM	Alcohol – Quantity, Frequency and Maximum Consumption (ALC-QFM)
AR	Adverse Reaction
ARC	Addiction recovery clinic
BUP-SL	BUP-sublingual
BUP-SL-NX	BUP-Sublingual-Naloxone (Suboxone®)
BUP-XR	BUP- Extended-Release (US Sublocade®; prev. RBP-60000)
CEQ-F – C	Craving Experience Questionnaire (frequency version) (Cocaine)
CEQ-F – H	Craving Experience Questionnaire (frequency version) (Heroin)
CGI-I	Clinical Global Impression (improvement)
CGI-S	Clinical Global Impression (severity)
CI	Chief Investigator
CONSORT	Consolidated Standards of Reporting Trials
CRA	Clinical Research Associate
CTIMP	Clinical Trial of Investigational Medicinal Product
CTU	Clinical Trials Unit
CUD	Cocaine Use Disorder
DERS-SF	Difficulties in Emotion Regulation Scale – Short Form

DSM5	Diagnostic and Statistical Manual of Mental Disorders 5th Edition
DMC	Data Monitoring Committee
eCRF	Electronic case report form
EDC	Electronic data capture
ESP	ESPranor®
EQ-5D-5L	EurolQol Health Status (5 level)
EXPO	Extended-release Pharmacotherapy for Opioid Use Disorder
GCP	Good clinical practice
GLM	Generalised Linear Model
HEAP	Health Economics Analysis Plan
IMP	Investigational Medicinal Product
ITT	Intention to Treat
KCF	Keyworker Contact Form
LFT	Liver Function Tests (AST, ALT, albumin and bilirubin)
MET	METHadone (oral)
mitt	modified Intention to Treat
MoCA	Montreal Cognitive Assessment
NHS	National Health Service
NWORTH	North Wales Organisation for Randomised Trials in Health
OUD	Opioid Use Disorder
PRO-I	Patient Reported Outcome (improvement)
PRO-S	Patient Reported Outcome (severity)
PSI	Personalised Psychosocial Intervention
QIDS-SR	Quick Inventory of Depressive Symptomatology
SAE	Serious Adverse Event
SAP	Statistical Analysis Plan
SAR	Serious Adverse Reaction
SCID-5-RV	Standard Clinical Interview for Dependence – Research Version (DSM-5)
SD	Standard Deviation
SURE	Substance Use Recovery Evaluator
SUSAR	Suspected Unexpected Serious Adverse Reaction
TLFB	Timeline Follow Back
TMG	Trial Management Group.
TOP	Treatment Outcomes Profile
TSC	Trial Steering Committee
UDS	Urine drug Screen
USA	United States of America
VAS-N (H/C)	Visual Analogue Craving Rating (Need) (heroin/cocaine)
VAS-W (H/C)	Visual Analogue Craving Rating (Want) (heroin/cocaine)
VIF	Variance Inflation factor
WSAS	Work and Social Adjustment Scale

